7 ENDPOINTS AND COVARIATES

7.1 EFFICACY/ EFFECTIVENESS ENDPOINT(S)

7.1.1 PRIMARY ENDPOINTS

Number and timing of treatment escalations of tofacitinib patients in 24 months, where Treatment Escalation in this study is defined as a switch to another DMARD or combination of DMARDs when compared to the last visit.

The following types of escalations will be distinguished:

1. Treatment **Termination**, which is the termination of a DMARD (or multiple when on combination therapy) without starting a new DMARD therapy. Premature study terminations (without documented treatment termination) will not be considered treatment terminations.
2. Treatment **Step-up** which is an increase from the current treatment regime towards e.g. a combination of DMARDs
3. Treatment **Step-down**, which is a de-escalation from the current treatment regime, e.g. from combination therapy to monotherapy

Patients start their therapy at baseline with tofacitinib either in Monotherapy or in Combination therapy with MTX. Subsequent therapy changes are documented on eCRF instrument “Rheumatologische Medikation“ by:

- adding additional DMARDs on top of the current therapy
- stopping the current DMARD in monotherapy and adding a new DMARD
- stopping one of multiple DMARDs when on combination therapy
- stopping one of multiple DMARDs when on combination therapy and adding a new DMARD
- stopping all DMARDs and not starting a new therapy. The escalation types depend on the combination of DMARD classes (tsDMARD vs bDMARD vs TNFi vs csDMARD). The eCRF does not explicitly distinguish between tsDMARD vs bDMARD vs TNFi, but combines all rheumatic medications belonging to the above classes under

tsDMARD/bDMARD. For the definition of treatment escalations, the following assignment of rheumatic medication to DMARD classes will be done:

tsDMARDs:

- baricitinib
- upadacitinib
- filgotinib

TNFi:

- etanercept
- adalimumab
- certolizumab
- golimumab
- infliximab

bDMARDs (excluding TNFi):

- abatacept
- rituximab
- anakinra
- tocilizumab
- sarilumab

For details of treatment escalations, e.g., which DMARD class addition or reduction leads to a particular escalation type, see table 12.2 in section 12.1.2.

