7.1.2.10 DRUG SURVIVAL STATUS OF TOFACITINIB

For patients who terminate tofacitinib, the drug survival status will be recorded as follows:

Those who terminate tofacitinib:

- Status = 1
- Time = Termination date tofacitinib – Date of initiation on tofacitinib

Tofacitinib is terminated when indicated on instrument “Rheumatologische Medikation” for therapy class tsDMARD/bDMARD variable *Change* (BDCM.CHANGECD) is set to “Therapy stop”. Tofacitinib pauses, where variable *Change* is set to “Therapy paused”, are not considered terminations.

Patients who do not terminate tofacitinib:

- Status = 0
- Time = Date of final visit – Date of initiation on tofacitinib

If patient is lost to follow-up or withdraws from the study they will be censored at the date of their last visit.

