7.3.3 POTENTIAL CONFOUNDERS TO BE INCLUDED IN THE PRIMARY ANALYSIS

A number of potential confounders will also be included in the primary analysis and all sensitivity analyses:

- Age at baseline
- Gender
- Duration of disease at baseline
- Indicator of tofacitinib dose
 - 1 if recommended dose of 5mg per day (i.e. TofInterval = BID),
 - 0 if reduced dose of 2.5mg per day (i.e. TofInterval = Daily).
- Poor prognostic factors (PF) indicator (1 if at least one Poor PF is present, 0 otherwise)
- Indicator of dose of MTX or combination partner (1 if increase in dose since last visit, 0 otherwise)
- Indicator of dose of Glucocorticoids (1 if increase in dose since last visit, 0 otherwise)
- Whether patient on 2nd or 3rd line treatment (see below)

A patient is defined as on 2nd line treatment if they were prescribed only csDMARDs prior to enrolling in the study.

A patient is defined as on 3rd line treatment if they were prescribed bDMARDs prior to enrolling in the study.

For a list of the medications considered to be csDMARDs and bDMARDs please see the eCRF.

- Indicator of tolerability issues (1 if treatment termination due to tolerability issues, 0 otherwise).
- Indicator of efficacy issues (1 if treatment termination due to efficacy issues, 0 otherwise).
- Incidence of the following comorbidities documented at the baseline visit (a term will be fitted for each comorbidity with the value 1 if the comorbidity is recorded for a patient or 0 otherwise):
 - Ischemic cardiovascular disease
 - Malignancies
 - Infections
 - Gastro disease
 - Osteoporosis
 - Depression

Any other variables observed to be potential confounders will also be investigated.

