8 HANDLING OF MISSING VALUES

8.1 TIME TO EVENT (PRIMARY ANALYSIS, TIME TO FIRST TREATMENT ESCALATION AND DRUG SURVIVAL)

Time to event should be determined for the events without any date imputation.

If a patient experiences the event of interest the status will be 1, and the time will be the time at which the event occurred (or visit at which it was recorded).

If a patient doesn't experience the event of interest the status will be 0, and the time will be the last time that the patient was known to be in the study (last visit). If this is not the end of the study then the time will be censored at this time point.

The primary endpoint is a time-to-event endpoint, although it takes into account the possibility of multiple events occurring for each patient. For each patient the data for analysis should consist of the times at which they experienced the event of interest and the values of the covariates at each time point. Any missing data within the covariates to be included in the models for primary analysis will be replaced by the nearest available value to the event. If more than one value qualifies, the later value will be used .

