12.1.2 DEFINITION OF TREATMENT ESCALATIONS

Table 11.2 provides an overview of all possible treatment switch combinations relevant for the analysis of the primary endpoint and defines the type of escalations, e.g., whether the treatment switch relates to a step-up, step-down or termination.

Table 12.2: Definition of treatment escalations

Therapy*	Mono Tofa	Mono tsDMARD	Mono csDMARD	MonoTNFi	Mono bDMARD	Combo+ csDMARD	Combo tsDMARD +csDMARD	ComboTNFi +csDMARD	Combo bDMARD+ csDMARD	Therapy Stop
MonoTofa	-	Step-up		Step-down	Step-up	Step-up	Step-up	Step-up	Step-up	Treatment termination
Mono tsDMARD	Step-up	Step-up if different tsDMARD		Step-down	Step-up	Step-up	Step-up	Step-up	Step-up	Treatment termination
Mono csDMARD	Step-up	Step-up	Step-up if different csDMARD		Step-up	Step-up	Step-up	Step-up	Step-up	Treatment termination
MonoTNFi	Step-up	Step-up		Step-down	Step-up if different TNFi	Step-up	Step-up	Step-up	Step-up	Treatment termination
Mono bDMARD	Step-up	Step-up		Step-down	Step-up	Step-up if different bDMARD	Step-up	Step-up	Step-up	Treatment termination
Combo+ csDMARD	Step- down	Step-up		Step-down	Step-up	Step-up	Step-up if different csDMARD	Step-up	Step-up	Treatment termination
Combo tsDMARD +csDMARD	Step-up	Step-up if different tsDMARD; Step-down otherwise		Step-down	Step-up	Step-up	Step-up if different tsDMARD or csDMARD	Step-up	Step-up	Treatment termination
Combo TNFi + csDMARD	Step-up	Step-up		Step-down	Step-down, if same TNFi, Step-up if different TNFi	Step-up	Step-up	Step-up if different csDMARD/TN Fi	Step-up if different bDMARD or csDMARD	Treatment termination
Combo bDMARD+ csDMARD	Step up	Step up		Step down	Step up	Step down if same bDMARD; Step-up otherwise	Step up	Step up	Step up	Step up if different bDMARD or csDMARD
*) Definitions:			Mono tsDMARD= Monotherapy any tsDMARD other than Tofa Mono csDMARD= Monotherapy any csDMARD Mono TNFi= Monotherapy any TNFi Mono bDMARD= Monotherapy any bDMARD other than TNFi Combo Tofa= Combination therapy tofacitinib with any csDMARD Combo csDMARD= Combination therapy tofacitinib + any csDMARD				Combo tsDMARD + csDMARD= Combination therapy tsDMARD other than tofacitinib + any csDMARD Combo TNFi + csDMARD= Combination therapy any TNFi+ any csDMARD Combo bDMARD + csDMARD= Combination therapy bDMARD other than TNFi+ anycsDMARD			

PPD

PPD

PPD

LEGAL DISCLOSURE

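### All six primary-endpoint Cox models adjust for treatment-termination indicators that are part of the outcome and carry no timing rule

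*SAP*

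**What the plan says.** **Outcome.** SAP 7.1.1 distinguishes three escalation types. The first is termination, "which is the termination of a DMARD (or multiple when on combination therapy) without starting a new DMARD therapy". SAP 12.1.2 classifies every change by "whether the treatment switch relates to a step-up, step-down or termination". SAP 9.1.1 fits the recurrent-event Cox model overall and for each type.

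**Covariates.** SAP 7.3.3 lists confounders for the primary analysis and every sensitivity analysis. Two of them are "Indicator of tolerability issues (1 if treatment termination due to tolerability issues, 0 otherwise" and "Indicator of efficacy issues (1 if treatment termination due to efficacy issues, 0 otherwise". Both appear in all six treatment-escalation rows of 9.2.6: primary, continuous-DAS28 and prior-visit, each on FAS and PPAS.

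**Timing.** A neighbouring entry has a window: "Indicator of dose of MTX or combination partner (1 if increase in dose since last visit, 0 otherwise". Comorbidities are tied to baseline. The two termination indicators have no time reference. The general rule in SAP 8.1 is that each patient contributes "the times at which they experienced the event of interest and the values of the covariates at each time point". A missing covariate "will be replaced by the nearest available value to the event", the later one if tied.

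**A second meaning of termination.** SAP 7.1.2.10 is wider: "Tofacitinib is terminated when indicated on instrument" Rheumatologische Medikation by a therapy-stop entry, whether or not another DMARD follows. SAP 7.3.3 does not say which meaning applies.

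**Protocol.** Sections 7.6.5 and 7.6.19 collect the reason for a switch or discontinuation and name two: lack of efficacy and intolerance. Table 6 lists tolerability as a potential confounder. It lists no variable for stopping because of inefficacy.

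**The concern.** A confounder precedes both factor and outcome. These indicators record the outcome itself, split by reason. The study asks whether disease activity, pain, the global assessments and satisfaction drive treatment change, and stopping for lack of efficacy is one of the ways in which they would do so. Conditioning on it removes part of the effect being estimated.

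The planned outputs would not reveal the problem. SAP 9.1.1 presents no estimates for confounders, so a very large or diverging indicator coefficient would not be tabulated. All sensitivity rows carry the same two indicators. The collinearity exploration in 9.2.2 is not aimed at a covariate built from the outcome. The first interim analysis covered secondary endpoints only, and the later ones did no modelling.

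**Working it through.** The plan gives no figure for this point, so the size was obtained by simulation.

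**1. Inputs.** From protocol 7.7: 1500 patients; P(LDA) = 0.2; P(change in DAS28 > 1.8) = 0.6; three normal VAS changes with the printed SDs; log-HRs −0.288, −2.303, −0.01, −0.01, −0.01; baseline 3.16 events per patient. Assumed: 8 quarterly intervals, at most one event per interval in visit-level runs, flags random among events, 70/30 efficacy/tolerability, and 10%, 20% or 40% of events flagged. Satisfaction was not simulated because the protocol gives no distribution for it.

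**2. Event counts.** The mean rate multipliers are:
- LDA: 0.8 + 0.2·exp(−0.288) = 0.950
- change in DAS28: 0.4 + 0.6·exp(−2.303) = 0.460
- VAS, centred: exp[½·0.01²·(38.579² + 30.966² + 24.672²)] = exp(0.153) = 1.165

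With centred VAS, 3.16 × 0.950 × 0.460 × 1.165 ≈ 1.61 events per patient, or about 2,400 in total (about 1,910 under the one-per-interval limit). The printed VAS means multiply this by exp[0.01·(29.31 + 27.01 + 34.99)] = exp(0.913) = 2.49, giving about 4.0 per patient (about 3,640 events under the limit).

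**3. Overall model.** Loss = 1 − (mean coefficient with flags ÷ mean coefficient without), as the range over the five factors:

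| Setting | 10% flagged | 20% | 40% |
|---|---|---|---|
| Same row, Breslow, VAS centred (300 replicates) | 3.4–6.2% | 7.5–13.1% | 18.2–28.8% |
| Same row, Efron, VAS centred (200) | 3.8–7.4% | 8.2–15.5% | 19.7–33.1% |
| Same row, Breslow, printed VAS means | 3–4% | 6–9% | 15–20% |
| Same row, Efron, printed VAS means | 3–5% | 7–11% | 17–26% |
| Same row, PWP gap-time (60) | 3.4–6.8% | 7.4–12.7% | 18.2–28.7% |
| Same row, continuous dates, Andersen-Gill (12) | 4–7% | 8–14% | 19–36% |
| Patient-ever, factors redrawn each visit | 0.7–1.5% | 1.5–2.8% | 3.0–5.6% |
| Patient-ever, factors fixed in patient | 3.4–6.1% | 7.6–12.2% | 18.5–24.2% |

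Flags from earlier terminations only: at most 0.4%, away from null. Discrete-tie likelihood: within about 2% of no change. Monte Carlo error is at most 0.7 points in the first row, but up to 3.6 points for LDA with continuous dates.

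A second simulation, with within-patient correlation 0.5 and about 1 event per patient, gave same-row losses of 4–9% at 10% flagged, 8–17% at 20% and 27–48% at 50%. Lagged flags caused none. The bias arises even when the reason is unrelated to the factors.

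**4. Hazard-ratio example (Breslow, centred).** Without flags, the coefficient for change in DAS28 > 1.8 is −2.066, so HR = 0.127. The input was −2.303 (HR 0.100); grouping by visit with Breslow ties has already cost 1 − 2.066/2.303 = 10.3%. The further loss due to flags is 7.5% at 20% flagged, exp(−2.066 × 0.925) = 0.148, and 18.2% at 40%, exp(−2.066 × 0.818) = 0.185.

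**5. Termination-type model.** Suppose every termination is flagged. The flagged rows are then exactly the event rows and the flag coefficients diverge. In the limit, a visit with d terminations and linear predictors η₁…η_d contributes, under Breslow ties, exp(Ση)/(Σexp η)^d. This is at most d^(−d), with equality only when all η are equal, so the factor coefficients go to 0. The simulation showed the same. With half the terminations flagged the loss is 30–49%.

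**6. Step-up and step-down models.** Under the 7.1.1 meaning, effects shift away from null by 1.7–3.7%, 3.5–6.9% and 5.5–11.0% when terminations are 10%, 20% and 30% of events. Under the 7.1.2.10 meaning (terminations 10% of events, all flagged), the step-up model loses 6–11%, 18–29% and 35–49% when 20%, 40% and 60% of step-ups are flagged.

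**7. Prior-visit rows.** If the flag moves with the event, the losses are 3.1–6.2%, 6.7–12.3% and 16.2–26.5% at 10%, 20% and 40% flagged. If it stays, they are below 3%.

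**The case against.** The SAP does not prescribe same-row coding. The fill-in rule in 8.1 is weak support for it: it covers missing values only, an indicator coded 0 otherwise is rarely missing, and four of the six rows in 9.2.6 specify no imputation. The row layout in 9.1.1 is described for the factors of interest, not for confounders. A programmer could lag the flags, which is harmless. The size depends on timing, meaning of termination, tie method and flagged share, none of them stated. Under 7.1.1, 40% flagged would require at least 40% of all escalations to be pure terminations. The centred-VAS figures exceed those at the printed means. The two reasons in protocol 7.6.5 concern a switch, and the eCRF option list is not visible, so complete flagging of terminations is a possibility only. SAP section 5 sets no decision rule, and the example hazard ratio stays strongly protective.

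These points stand as limits on size and certainty. They do not remove the defect. The general rule of covariate values at each time point still leads to the same-row flag, patient-ever coding biases as well, and nothing in the text selects the lagged version. Different readings give different hazard ratios for the primary objective.

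**Conclusion.** The concern holds. The plan conditions on part of its own outcome in all six primary-endpoint rows. With same-row or patient-ever flags, factor hazard ratios in the overall model move toward 1 under Breslow or Efron ties or with continuous dates, in both models that 9.1.1 allows. For same-row flags under Breslow or Efron ties the loss of log-HR is about 3–7%, 6–16% and 15–33% at assumed flagged shares of 10%, 20% and 40%, so a small share means a small bias. Standard errors change by at most 6%. No loss of power is claimed, and nothing is quantified for satisfaction. The termination-type model fails if every termination carries one of the two reasons. Confidence in the direction is good for those tie methods; confidence in the size is moderate because the flagged share is unknown.

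**What to change.** In SAP 7.3.3 and all six rows of 9.2.6, rule out same-row and patient-ever termination flags. Then choose one of two options:

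- Delete both indicators.
- Define each as 1 if a termination for that reason is dated before the start of the interval, and 0 otherwise. This keeps the tolerability confounder of protocol Table 6.

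Also state in 7.3.3 whether termination has the 7.1.1 or the 7.1.2.10 meaning, and name the tie method in 9.1.1. If the reason for stopping is of interest, analyse it as an outcome in supportive cause-specific models (lack of efficacy; intolerance), with other or missing reasons as a separate category.

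The cost is SAP wording and a changed derivation of two covariates. Stop dates and reasons for switch are already collected under protocol 7.6.5.

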8 HANDLING OF MISSING VALUES

8.1 TIME TO EVENT (PRIMARY ANALYSIS, TIME TO FIRST TREATMENT ESCALATION AND DRUG SURVIVAL)

Time to event should be determined for the events without any date imputation.

If a patient experiences the event of interest the status will be 1, and the time will be the time at which the event occurred (or visit at which it was recorded).

If a patient doesn't experience the event of interest the status will be 0, and the time will be the last time that the patient was known to be in the study (last visit). If this is not the end of the study then the time will be censored at this time point.

The primary endpoint is a time-to-event endpoint, although it takes into account the possibility of multiple events occurring for each patient. For each patient the data for analysis should consist of the times at which they experienced the event of interest and the values of the covariates at each time point. Any missing data within the covariates to be included in the models for primary analysis will be replaced by the nearest available value to the event. If more than one value qualifies, the later value will be used .

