7.12. Limitations of the research methods

Randomised controlled trials are important and powerful tools in assessing efficacy and safety but have their limitations in terms of generalisability. In order to assess health economics, clinical effectiveness and safety of Tofacitinib in a usual care setting, parameters need to be determined by performing observational studies.

Inherent limitations of non-interventional, observational, non-controlled, non-randomised studies in general are the risk of selection/ascertainment bias and some lack of a parallel control group, which complicate the interpretation of the causality between treatment and outcomes. Furthermore, as with any "as observed" analysis, there is a potential risk of bias due to missing outcome data; the risk increases with increasing number of missing outcome data.

As data captured will be limited to information available from the physician participating in the study under a usual care setting, there is a greater possibility that there will be individual items of missing data (e.g. CRP not measured or FFbH questionnaire not completed). Following up patients after treatment escalation, rather than discontinuing patients from the study when they switch from Tofacitinib, should result in a higher proportion of the patients remaining in the study until the planned completion date. Where data are missing, information from the patient at other visits may be used in the primary analysis model to assess predictors of treatment decisions. If the different factors being considered in the primary statistical model to look at impact of treatment change are highly correlated it may not be clear which of the factors is in fact driving the rate of treatment escalation. Other sensitivity analyses may be explored to assess the impact of any confounding. Further details will be included in the SAP.

Patients selected for study inclusion represent a population who are initiated on Tofacitinib as part of a usual care setting. The sample of patients will be obtained from physicians who are willing to participate in the study and there is a possibility that certain types of patients will be selected to be prescribed Tofacitinib (selection bias) and join the study and this could potentially have an impact on findings of the primary analysis (if the 'type' is expected to impact the rate of treatment escalation). Therefore, study findings may not be generalizable to all RA patients.

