7.1.2.4 CHANGE FROM BASELINE IN DAS28-4 (ESR) AND DAS28-4 (CRP)

7.1.2.4.1 DAS28-4

$\text{DAS28-4 (ESR)} = 0.56*\sqrt{(\text{TJC28})} + 0.28*\sqrt{(\text{SJC28})} + 0.70*\ln(\text{ESR in mm/ hour}) + 0.014*\text{PtGA in mm.}$

DAS28-4 (CRP) is similarly calculated by:

$\text{DAS28-4 (CRP)} = 0.56*\sqrt{(\text{TJC28})} + 0.28*\sqrt{(\text{SJC28})} + 0.36*\ln(\text{CRP in mg/l} + 1) + 0.014*\text{PtGA in mm} + 0.96$

Where TJC28 is the Tender Joint Count, SJC28 is the Swollen Joint Count, CRP is the C-reactive protein in mg/L, ESR is the Erythrocyte Sedimentation Rate in mm/first hour and

PtGA is the Patient's Global Assessment of Health in mm. PtGA will be used in this calculation.

The change from baseline in DAS28-4 (ESR) will be calculated at each time point as:

DAS28-4 (ESR) at time point – DAS28-4 (ESR) at baseline.

Similarly change from baseline in DAS28-4 (CRP) will be calculated at each time point as:

DAS28-4 (CRP) at time point – DAS28-4 (CRP) at baseline.

Change from Baseline in DAS 28-4 at all time points (M3, M6, M9, M12, M15, M18, M21, M24) will be presented.

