7.3 COVARIATES, FACTORS AND POTENTIAL CONFOUNDERS

7.3.1 FACTORS OF INTEREST FOR PRIMARY ANALYSIS

The following covariates will be included in the primary analysis:

- a. DAS 28-4 (ESR) LDA (see sections 6.1.2.4.1 and 6.1.2.2.3 for derivations) [Note: this is a binary endpoint].
- b. Indicator variable for whether patient has achieved change from baseline of DAS28-4 (ESR) > 1.8 (see section 6.1.2.4.1 for derivations of DAS28-4 (ESR)) [Note: this is a binary endpoint].

Change from baseline will be calculated as:

$\Delta\text{DAS28-4 (ESR)} = \text{DAS28-4 (ESR) at time point} - \text{DAS28-4 (ESR) at baseline}$

If a patient has achieved $\Delta\text{DAS28-4 (ESR)} > 1.8$ the indicator will be 1,

If $\Delta\text{DAS28-4 (ESR)} > 1.8$ is not achieved, the indicator will be 0.

- c. Physician Global Assessment of Arthritis – measured on a visual analogue scale (0-100mm).
- d. Patient's Global Assessment of Arthritis – measured on a visual analogue scale (0-100mm).
- e. Patient's Assessment of Arthritis Pain – measured on a visual analogue scale (0-100mm).
- f. Patient's overall satisfaction with treatment:

For each patient the response to the question ‘How satisfied are you with the drugs that you have received for your arthritis since your last visit?’ will be assigned as below:

0 = extremely dissatisfied,

1 = dissatisfied,

2 = neither satisfied nor dissatisfied,

3 = satisfied

4 = extremely satisfied

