8.3 CONTINUOUS ENDPOINTS

Missing data will not be imputed unless stated otherwise.

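### If one DAS28 component is missing, the SAP's nearest-value rule can take both DAS28 factors from another visit, possibly after the switch, and may distort them in the primary model

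*SAP*

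**What the plan says.** SAP 8.1 sets the rule for the primary model: "Any missing data within the covariates to be included in the models for primary analysis will be replaced by the nearest available value". Nearness is judged from the event. On ties it says: "If more than one value qualifies, the later value will be used". It gives no maximum distance in time and does not mention the components of a composite score.

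SAP 7.3.1 lists six factors. The two DAS28 factors are derived flags: the LDA flag, and the "Indicator variable for whether patient has achieved change from baseline of DAS28-4 (ESR) > 1.8". The other four are PhyGA, PtGA, pain and satisfaction. ESR and the joint counts are not covariates in their own right.

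SAP 7.1.2.4.1 builds DAS28-4 (ESR) from TJC28, SJC28, ESR and PtGA and has no rule for a missing component. For continuous endpoints, SAP 8.3 says: "Missing data will not be imputed unless stated otherwise". Protocol 7.12 foresees that "there will be individual items of missing data (e.g. CRP not measured or FFbH questionnaire not completed"), and allows information from a patient's other visits to be used in the primary model.

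The table in SAP 9.2.6 marks the FAS primary model and the FAS prior-visit sensitivity run as imputed. It marks as not imputed both PPAS runs of the binary-factor model (primary and prior-visit) and the continuous-DAS28 model in the FAS and the PPAS.

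**The concern.** The study asks whether DAS28 or something else drives the rheumatologist's decision. DAS28 becomes unavailable when any one of four items is missing. PhyGA, pain and satisfaction are each lost only with their own item. A rule that works on the derived flags therefore makes DAS28 the factor most exposed to values from another date. When only ESR is missing, the competing scores in the same row are current.

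Such a row can also hold two PtGA values: the current one as its own factor, and another visit's PtGA inside the borrowed DAS28. If borrowed flags are often wrong, a real DAS28 effect can look weaker than it is, and correlated scores can absorb part of it. LDA has little room for this, because Protocol 7.7 puts its power at only around 50% with 1500 patients.

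**Working it through.** **1. The plan's own figure.** No figure in the documents involves the fill rule. The nearest is the LDA power of around 50% at N = 1500 (Protocol 7.7), with coefficient −0.288, LDA prevalence 0.2 and 3.16 baseline events per patient. Two-sided 0.05 is assumed.

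- The approximation power = Φ(|β|·√(D·p(1−p)) − 1.96) gives 50% when D = 1.96² / (0.288² × 0.2 × 0.8) ≈ 289 events.
- The stated inputs give about 4.01 events per patient, so D ≈ 6,014. Then 0.288 × √(6,014 × 0.16) ≈ 8.9, and power is near 100%.

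The 50% is therefore not reproduced. The full simulation settings are not in the documents, so this does not show an error, and it does not bear on the fill rule.

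**2. Which visit donates.** Assume the decision falls on a target day in SAP 12.1.1 (days 1, 91, 182, 273, 365, 456, 547, 638, 730) and both neighbouring visits are on their target days with DAS28 available.

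| Visit with missing ESR | Days to earlier / later visit | Donor |
|---|---|---|
| M3 | 90 / 91 | earlier |
| M6 | 91 / 91 | later (tie) |
| M9 | 91 / 92 | earlier |
| M12 | 92 / 91 | later |
| M15 | 91 / 91 | later (tie) |
| M18 | 91 / 91 | later (tie) |
| M21 | 91 / 92 | earlier |

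At four of these seven visits the donor is later, so it reflects the patient after the switch.

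**3. Simulation A.** All inputs are assumed unless marked: 1500 patients (Protocol), 8 visits, 39% in LDA, correlation between visits 0.6 (joint counts, VAS) and 0.7 (ln ESR), ESR missing at random, true LDA hazard ratio 0.50, no PhyGA effect. The model is discrete-time complementary log-log with LDA, PhyGA, PtGA and pain; 150 replicates in the main settings.

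| ESR missing | LDA HR, whole score borrowed | LDA HR, ESR only filled | PhyGA falsely significant (whole / ESR only) |
|---|---|---|---|
| 10% | 0.54 | 0.51 | 5% / 5% |
| 30% | 0.62 | 0.54 | 36% / 9% |
| 50% | 0.71 | 0.58 | 67% / 9% |

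- In filled rows the LDA flag was wrong in 28–30% (whole score) against 10–12% (ESR only).
- At 30% missing, the root-mean-square error of the filled DAS28 was 1.15 against 0.46.
- With correlations 0.4/0.6 and 0.8/0.8 at 30% missing, the LDA HR was 0.65 and 0.59, against 0.55 and 0.54.
- At the planning effect, exp(−0.288) = 0.75, with 30% missing, it was 0.83 against 0.78, with no excess of PhyGA false positives.

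**4. Simulation B.** Assumed: 12 runs of 4000 patients, 9 quarterly visits, latent correlation 0.7, disease activity falling after a switch, about 1.2 events per patient, LDA prevalence about 0.32, LDA coefficient −0.288 (Protocol), change-flag coefficient −1.0, change flag coded as improvement above 1.8. The model is again complementary log-log, with all six factors. Loss = 1 − (coefficient after fill / coefficient with full data).

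| ESR missing at random | Full data | Whole score borrowed | ESR only filled | Loss, whole / ESR only |
|---|---|---|---|---|
| 10% | −0.299 | −0.199 | −0.291 | 34% / 3% |
| 20% | −0.249 | −0.110 | −0.229 | 56% / 8% |
| 40% | −0.261 | −0.008 | −0.220 | 97% / 16% |

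At 10/20/40% missing with whole-score borrowing:

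- the change-flag coefficient lost 15/26/43%;
- PtGA rose 8/13/25% and PhyGA 6/9/16%; pain and satisfaction moved by about 6% or less;
- borrowed LDA status agreed with the truth at about 75% of filled visits, against 90% with ESR-only fill.

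**5. Dependence on the assumptions (simulation B, whole-score borrowing).**

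- LDA coefficient −0.7: losses of 23/39/71%.
- ESR missing more often when PhyGA is low: losses of 25–30%.
- ESR missing more often at escalation visits: 81% loss (true −0.7), or a change of sign to +0.086 (true −0.288).
- Complete cases stayed close to full data for the DAS28 factors throughout.

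**6. Translation to power.** If full-data power is the stated 50% and the standard error does not change, power = Φ(1.96·r − 1.96), where r is the fraction of the coefficient retained. For r = 0.66, 0.44 and 0.03 this gives about 25%, 14% and 3%. For ESR-only fill, r = 0.97, 0.92 and 0.84 gives about 48%, 44% and 38%.

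**The case against.** A reader might infer that the SAP prescribes whole-score borrowing. It does not say so. SAP 8.1 is silent on whether a missing ESR is filled before DAS28 is derived. SAP 8.3 concerns continuous endpoints and leaves room for exceptions, so it does not forbid a component fill. This stands: whole-score borrowing is the plain reading of a rule on covariates, not a stated instruction.

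A reader might also infer that the rule biases DAS28 toward no effect and favours the physician and patient scores as a matter of course. The documents do not support that. The protocol's examples of missing items are CRP and FFbH, and neither enters DAS28-4 (ESR). No document gives an ESR missing rate. In simulation A the excess of PhyGA false positives was absent at 10% missing, and at the planning hazard ratio with 30% missing. In simulation B the sign could reverse. Simulation A also omits two of the six factors, and neither simulation includes the planned confounders or fits the planned recurrent-event Cox model.

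The planned no-imputation runs are a real safeguard, since complete cases did well in simulation B. But for the binary-factor model they exist only in the PPAS, which also changes which visits count, and the FAS run uses continuous DAS28. No planned run isolates the fill rule in the primary model and its population. Nor is same-visit PtGA lost from the model; it is lost only from the filled DAS28 flags.

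**Conclusion.** The point holds in a qualified form. On the plain reading, one missing component moves both DAS28 flags to another visit, possibly after the switch, and leaves the decision visit's joint counts and PtGA out of them. This may bias the DAS28 factors, usually toward no effect when ESR is missing at random, with some shift to PtGA or PhyGA. Under random missingness, both simulations found clearly more attenuation with whole-score borrowing than with component fill.

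The magnitudes are illustrative only. They rest on an assumed ESR missing rate, visit-to-visit correlation and missingness mechanism, none of which the documents give, and the mechanism alone can change the sign. The component fill is better under these assumptions and cheap, so the SAP should adopt it.

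**What to change.** In SAP 8.1:

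- State that only the missing DAS28 component is filled. DAS28-4 (ESR), the LDA flag and the change flag are then recomputed with the components recorded at the visit itself.
- Restrict donor values to those dated on or before the treatment switch, and state a maximum age for them.

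In SAP 9.2.2 and 9.2.6, add a no-imputation run of the binary-factor primary model in the FAS.

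No new data are needed; the cost is SAP wording and a little programming. The downsides are that a borrowed ESR mixes dates within one score, some rows may stay missing under the age limit, and the age limit itself has to be chosen.
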